#### **5.9 Contraception**

Patients with partners of child bearing potential, who are sexually active, must agree to the use of two highly effective forms of contraception throughout period of taking study treatment and for 3 months after last dose of study drug.

For details refer to Appendix E Acceptable Birth Control Methods.

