$$\text{Estimated creatinine clearance} = \frac{(140 - \text{age [years]}) \times \text{weight (kg)}}{\text{serum creatinine (mg/dL)} \times 72}$$

Note: Patients with creatinine clearance between 51- 80 mL/min either at trial enrolment or during the course of the trial should be monitored every 2 weeks for laboratory assessment and toxicity evaluation.

- ECOG Performance Status  $\leq 2$  (Appendix A: Performance Status Criteria)
- Participants must have a life expectancy  $\geq 12$  months.
- Male participants and their partners, who are sexually active and of childbearing potential, must agree to the use of two highly effective forms of contraception in combination [see appendix E for acceptable methods], throughout the period of taking study treatment and for 6 months after last dose of study drug to prevent pregnancy in a partner.

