**7.1.9 *Pregnancy***

Male participants should refrain from fathering a child or donating sperm during the study and for 6 months following the last dose.

Pregnancy of the patient's partners is not considered to be an adverse event. However, the outcome of all pregnancies (spontaneous miscarriage, elective termination, ectopic pregnancy, normal birth or congenital abnormality) should if possible be followed up and documented.

The outcome of any conception occurring from the date of the first dose until 6 months *after the last dose* should be followed up and documented.

All outcomes of pregnancy should be reported to Clovis Oncology.

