## APPENDIX E. ACCEPTABLE BIRTH CONTROL METHODS

Rucaparib is regarded as a compound with medium/high fetal risk. Subjects with partners of childbearing potential, who are sexually active, must agree to the use of TWO highly effective forms of contraception (defined as a method that can achieve a failure rate of <1% per year when used consistently and correctly) in combination [as listed below], throughout the period of taking study treatment and for at least 4 month after last dose of study drug(s), or they must totally/truly abstain from any form of sexual intercourse (see below).

Highly Effective Non-hormonal birth control methods include:

- Total sexual abstinence. Abstinence must continue for the total duration of study treatment and for at least 1 month after the last dose. Periodic abstinence (eg, calendar ovulation, symptothermal post ovulation methods) and withdrawal are not acceptable methods of contraception.
- Vasectomised sexual partner PLUS male condom. With participant assurance that partner received post-vasectomy confirmation of azoospermia.
- Tubal occlusion PLUS male condom
- IUD PLUS male condom. Provided coils are copper-banded

Highly Effective hormonal methods:

- Normal and low dose combined oral pills PLUS male condom
- Cerazette (desogestrel) PLUS male condom. Cerazette is currently the only highly efficacious progesterone based pill.
- Hormonal shot or injection (eg., Depo-Provera) PLUS male condom
- Etonogestrel implants (e.g., Implanon, Norplant) PLUS male condom
- Norelgestromin / EE transdermal system PLUS male condom
- Intrauterine system [IUS] device (eg., levonorgestrel releasing IUS -Mirena®) PLUS male condom
- Intravaginal device (e.g., EE and etonogestrel) PLUS male condom.

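### Section 5.9 ends contraception 3 months after the last dose and Appendix E sets minimums of 4 months (1 for abstinence), while Sections 3.3 and 7.1.9 set 6 months

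*Combined protocol and SAP*

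**What the plan says.** Four places in the protocol say how long a man must avoid conception after stopping rucaparib.

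- **Section 3.3 (Inclusion Criteria)** requires agreement to two highly effective methods. It sends the reader to the appendix for the methods and states the duration itself: "see appendix E for acceptable methods], throughout the period of taking study treatment and for 6 months after last dose of study drug".
- **Section 5.9 (Contraception)** repeats the two-method requirement but limits it to treatment and "for 3 months after last dose of study drug". It then adds: "For details refer to Appendix E Acceptable Birth Control Methods".
- **Section 7.1.9 (Pregnancy)** says that male participants "should refrain from fathering a child or donating sperm during the study and for 6 months following the last dose". It also sets a follow-up window: "The outcome of any conception occurring from the date of the first dose until 6 months" after the last dose is to be followed up and documented.
- **Appendix E** gives a general minimum, "for at least 4 month after last dose of study drug(s", and a separate one for abstinence: "Abstinence must continue for the total duration of study treatment and for at least 1 month after the last dose". It opens with the statement "Rucaparib is regarded as a compound with medium/high fetal risk".

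**The concern.** Sections 3.3 and 5.9 place the same obligation on the same men and give different end dates. Section 5.9 carries the contraception heading, so staff counselling a man at the end of treatment are likely to look there, and it holds the shortest general duration. Appendix E, to which both sections point, adds two further figures, and no text gives one section precedence.

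A site that relied on Section 5.9, or on the minimums in Appendix E, could tell a man to stop protection before Sections 3.3 and 7.1.9 allow it. A conception after that advice would still fall inside the period that Section 7.1.9 wants followed up. Two sites are planned. They could follow different sections, and each could say that it had followed the protocol.

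The instruction matters in this trial. Appendix E rates the fetal risk as medium to high, and the Toxicology text in Section 1.2.2 reports rucaparib as clastogenic in vitro. The patients have declined, or cannot have, androgen deprivation, and must have a testosterone of at least 100 ng/dL.

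**Working it through.** The plan has no calculated figure to reproduce here. The check sets the stated durations side by side and subtracts.

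| Place | What is required | Months after last dose |
|---|---|---|
| Section 3.3 | two methods (eligibility condition) | 6 |
| Section 7.1.9 | no fathering a child, no sperm donation | 6 |
| Section 7.1.9 | follow-up of conceptions | up to 6 |
| Section 5.9 | two methods | 3 |
| Appendix E, general | two methods | at least 4 |
| Appendix E, abstinence | total abstinence | at least 1 |

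**Section 5.9 against Sections 3.3 and 7.1.9.** 6 − 3 = 3 months. A conception in months 4 to 6 would follow advice that complied with Section 5.9, yet lie inside the Section 7.1.9 follow-up window.

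**Appendix E general minimum against Sections 3.3 and 7.1.9.** 6 − 4 = 2 months (months 5 and 6). The appendix figure is a minimum, so a man who continues for 6 months satisfies it. It becomes a shortfall only if a site treats the minimum as the stopping point.

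**Section 5.9 against Appendix E.** 4 − 3 = 1 month. A period of 3 months cannot meet a minimum of 4, so Section 5.9 also conflicts with the appendix that it cites.

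**Within Appendix E.** 4 − 1 = 3 months between the general and the abstinence minimum. This is a difference in wording and not a gap in protection. A man who ends abstinence becomes sexually active and comes back under the contraception rules, including the 6 months in Section 3.3. For that reason the arithmetic 6 − 1 = 5 is not claimed as a shortfall.

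**Could the texts be reconciled?** The Appendix E minimums can be read together with 6 months. The 3 months in Section 5.9 cannot, because it is a flat duration for the same obligation. All four texts are current. The differences do not come from an amendment summary, from redaction or from reading the PDF.

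**The case against.** The strongest reply is that the stricter rule already applies. Section 3.3 cites Appendix E only for methods and gives its own duration in the same sentence. It is an inclusion criterion, so no man within its scope can enter without agreeing to 6 months, and Section 7.1.9 repeats that period. On this reading, harm needs a site to overlook two sections. Men are also counselled through the consent form, which was not available for this review and may already say 6 months. The documents do not show that 3 or 4 months is too short, and they do not say which duration is correct.

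Much of this stands. Agreement to 6 months at entry does reduce the risk, the consent form may be right, and no harm is demonstrated. The abstinence line is poor drafting and adds no exposure of its own. Section 7.1.9 is also worded as refraining from fathering a child or donating sperm, and not as a period of contraceptive use.

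The reply does not remove the conflict. What a man agrees to at screening can be undone by what he is told when treatment stops, and at that point the section named for contraception gives half the period. A correct consent form would leave the protocol still contradicting itself. If the sponsor thinks a shorter period is right, Sections 3.3 and 7.1.9 would have to change. Either way, the four places must agree.

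**Conclusion.** The concern holds, and the text is wrong as written. It is an internal inconsistency in a participant-safety instruction and not a deliberate design choice. The direct conflict is between Section 5.9 and Sections 3.3 and 7.1.9, and it amounts to 3 months. The general minimum in Appendix E leaves a possible shortfall of 2 months for a site that treats it as the end point.

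The conclusion rests on reading Section 5.9 as an operative instruction, which its wording supports. It applies only to sexually active men with partners of childbearing potential. The documents do not give their number, which cannot exceed the 30 patients planned in Section 3.2. The point has no bearing on the PSA response endpoint or on the two-stage design. It should be corrected because the rule protects third parties and the correction is easy.

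**What to change.** Make three wording changes: set the duration in Section 5.9, the general minimum in Appendix E and the abstinence minimum in Appendix E all to 6 months after the last dose. Six months is the period already used in the eligibility criterion and in the pregnancy section. It satisfies every minimum stated elsewhere, and it is the cautious choice where the documents do not settle which figure is right. Then check that the consent form gives the same period. The cost is a short text amendment and that check, with no change to sample size, endpoint or analysis.

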## **6. THERAPEUTIC/DIAGNOSTIC AGENT(S)/MODALITY(-IES)**

### **6.1 Description of Treatments**

The drug to be tested in this clinical protocol is rucaparib (IND #). Rucaparib will be supplied by Clovis Oncology.

### **6.2 Pharmacokinetics**

Dose proportional PK were observed up to 600 mg BID. The mean  $T_{max}$  and mean  $T_{1/2}$  were approximately 4 hours and 17 hours, respectively. Oral administration of 600 mg rucaparib with a high-fat meal resulted in a moderate increase of  $C_{max}$  and AUC of rucaparib compared with that under fasted conditions. The increases in rucaparib exposures were not considered clinically significant, thus rucaparib can be taken with or without food.

### **6.3 Dosage Selected, Preparation, and Schedule of Administration**

Rucaparib will be dosed based upon guidelines in Section 5. Treatment will be administered on an outpatient basis. Rucaparib is dosed twice daily. Patients will be asked to keep a drug diary and present bottles for assessment at each assessment.

#### *6.3.1 Supply, storage requirements, and special handling*

##### **6.3.1.1 Supply and packaging**

Rucaparib camsylate (formerly known as PF-01367338 and AG-014447) is an oral formulation with a molecular weight of 555.67 Daltons.

Rucaparib tablets for oral administration will be supplied by Clovis. A brief description of the investigational product is provided below.

Drug Name:	Rucaparib
INN:	Rucaparib
Formulation:	Tablet; film coated; 200 mg, 250 mg, 300 mg
How Supplied:	200, 250, and/or 300 mg strength (based on free base) in high-density polyethylene bottles or equivalent with child-resistant caps. Patients may receive 1 or more strengths. Each bottle contains 60 tablets

#### 6.3.1.2 Storage requirements

All tablets are provided in high-density polyethylene (HDPE) bottles with child-resistant caps and should be stored in the provided containers. between 15° and 30° C (59 and 86° F).

#### 6.3.1.3 Labeling

Labels will be prepared in accordance with Good Manufacturing Practice (GMP) and local regulatory guidelines. The labels will fulfill GMP Annex 13 requirements for labeling. Label text will be translated into local language.

### 6.4 Removing Patients from the Protocol

In the absence of treatment delays because of adverse events, treatment will continue for until one of the following criteria applies:

- Patient decision. The patient is at any time free to discontinue treatment, without prejudice to further treatment
- Severe non-compliance with the study protocol
- Bone marrow findings consistent with myelodysplastic syndrome (MDS)/acute myeloid leukaemia (AML)
- Potential Hy's Law cases (AST or ALT  $\geq 3 \times$  ULN and TBL  $\geq 2 \times$  ULN with no other reason)
- PSA doubling from baseline value, confirmed by a second value at least 4 weeks apart, with a minimum time since initiation of therapy of 12 weeks.
- Disease progression by symptomatic or radiographic assessment. Patient requiring palliative radiation therapy will be considered to have disease progression and removed from the study.
- Intercurrent illness that prevents further administration of treatment
- Unacceptable adverse events that may or may not be directly related to treatment but that, in the judgment of the treating physician, makes it dangerous for the patient to be retreated.
- Adverse events requiring cessation of rucaparib, with inability to restart therapy within 14 days.
- General or specific changes in the patient's condition that render the patient unacceptable for further treatment, in the judgment of the investigator

Because an excessive rate of withdrawals can render the study uninterpretable, unnecessary withdrawal of patients should be avoided. When a patient discontinues treatment early, the investigator should make every effort to contact the patient and to perform a final evaluation. The reason(s) for withdrawal should be recorded.

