#### **Management of AST/ALT Elevations**

Grade 3 ALT/AST elevations have been successfully treated with treatment interruption and/or a reduction in dose. The data reported as of the data cut-off date suggest that many patients have been able to continue treatment with 600 mg BID following a dose interruption, without any further elevation or recurrence of Grade 3 ALT/AST. The following guidelines have been suggested for managing Grade 3/4 ALT/AST elevations.

Grade 4 ALT/AST elevations: Patients should stop taking rucaparib until values have returned to Grade 2 or better, then resume rucaparib with a dose reduction to 500mg BID. Monitor liver function tests weekly for 3 weeks after rucaparib has been restarted. If a Grade 4 ALT/AST elevation is again observed at 500mg BID, Patients should stop taking rucaparib until values have returned to Grade 2 or better, then resume rucaparib with a dose reduction to 400mg BID. Dose reductions to 300mg BID will be allowed.

Grade 3 ALT/AST elevations, in the absence of other signs of liver dysfunction, should be managed as follows:

- Monitor liver function tests weekly until resolution to  $\leq$  Grade 2.
- Continuation of rucaparib with elevation of ALT/AST up to Grade 3 is permitted provided bilirubin is  $<$  ULN and alkaline phosphatase is  $< 3 \times$  ULN.
- If patient has Grade 3 ALT/AST and continues on rucaparib, and levels do not decline within 2 weeks or they continue to rise, treatment interruption and resolution to  $\leq$  Grade 2 will be required before rucaparib can be resumed, either at the at a reduced dose (500mg BID (if currently taking 600mg BID), 400mg BID (if currently taking 500mg BID), 300mg BID (if currently taking 400mg BID).

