### **2. DEFINITIONS**

#### **Potential Hy's Law (PHL)**

- Aspartate Aminotransferase (AST) or Alanine Aminotransferase (ALT)  $\geq$  3x Upper Limit of Normal (ULN) and Total Bilirubin (TBL)  $\geq$  2xULN at any point during the study irrespective of an increase in Alkaline Phosphatase (ALP).

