#### **Hy's Law (HL)**

- AST or ALT  $\geq$  3x ULN and TBL  $\geq$  2xULN, where no other reason, other than the IMP, can be found to explain the combination of increases, eg, elevated ALP indicating cholestasis, viral hepatitis, another drug.

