The instructions in this Section should be followed for all cases where PHL criteria are met. No later than 3 weeks after the biochemistry abnormality was initially detected, the Study Physician contacts the Investigator in order to review available data and agree on whether there is an alternative explanation for meeting PHL criteria other than DILI caused by the IMP. Clovis Oncology and the Principal Investigator will also be involved in this review together with other subject matter experts as appropriate. According to the outcome of the review and assessment, the Investigator will follow the instructions below.

If there is an agreed alternative explanation for the ALT or AST and TBL elevations, a determination of whether the alternative explanation is an AE will be made and subsequently whether the AE meets the criteria for a SAE:

- If the alternative explanation is not an AE, record the alternative explanation on the appropriate CRF
- If the alternative explanation is an AE/SAE, record the AE /SAE in the CRF accordingly and follow the Clovis Oncology standard processes

If it is agreed that there is no explanation that would explain the ALT or AST and TBL elevations other than the IMP:

- Report an SAE (report term 'Hy's Law') according to Clovis Oncology standard processes.
  - The 'Medically Important' serious criterion should be used if no other serious criteria apply
  - As there is no alternative explanation for the HL case, a causality assessment of 'related' should be assigned.

If, there is an unavoidable delay, of over 3 weeks, in obtaining the information necessary to assess whether or not the case meets the criteria for HL, then it is assumed that there is no alternative explanation until such time as an informed decision can be made:

- Report an SAE (report term 'Potential Hy's Law') applying serious criteria and causality assessment as per above
- Continue follow-up and review according to agreed plan. Once the necessary supplementary information is obtained, repeat the review and assessment to determine whether HL criteria are met. Update the SAE report according to the outcome of the review

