#### 6. *ACTIONS REQUIRED FOR REPEAT EPISODES OF POTENTIAL HY'S LAW*

This section is applicable when a patient meets PHL criteria on study treatment and has already met PHL criteria at a previous on study treatment visit.

The requirement to conduct follow-up, review and assessment of a repeat occurrence(s) of PHL is based on the nature of the alternative cause identified for the previous occurrence.

The investigator should determine the cause for the previous occurrence of PHL criteria being met and answer the following question:

- Was the alternative cause for the previous occurrence of PHL criteria being met chronic or progressing malignant disease?
  - If No: follow the process described in Section 4 of this Appendix
  - If Yes: Determine if there has been a significant change in the patient's condition# compared with when PHL criteria were previously met
    - If there is no significant change no action is required
    - If there is a significant change follow the process described in Section 4 of this Appendix

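### Section 6.4 removes Potential Hy's Law cases under Appendix F's Hy's Law criterion, and the Grade 4 ALT/AST rule, the cause review and the interruption limits are not reconciled with it

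*Combined protocol and SAP*

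**What the plan says.** **Section 6.4 (removal).** Treatment ends for "Potential Hy's Law cases (AST or ALT" at least 3 times ULN with total bilirubin at least 2 times ULN. The bracket closes with "ULN with no other reason". A separate bullet removes patients for "Adverse events requiring cessation of rucaparib, with inability to restart therapy within 14 days".

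**Appendix F, section 2 (definitions).** Potential Hy's Law (PHL) is the same pair of thresholds "at any point during the study irrespective of an increase in Alkaline Phosphatase (ALP"; no judgement of cause is needed. Hy's Law (HL) is the same pair "where no other reason, other than the IMP, can be found to explain the combination of increases".

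**Appendix F, sections 4 to 6 (process).** Section 5.2.1 sends sites here when ALT, AST or bilirubin crosses its threshold. Once PHL is met, the investigator notifies, monitors, investigates, completes forms and reports. On the cause review: "No later than 3 weeks after the biochemistry abnormality was initially detected, the Study Physician contacts the Investigator". If the information is delayed beyond 3 weeks, the absence of another explanation is assumed for the time being. Section 6 covers repeat episodes, "when a patient meets PHL criteria on study treatment and has already met PHL criteria at a previous on study treatment visit".

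**Section 5.4.2.1.2 (ALT/AST elevations).** For Grade 4: "Patients should stop taking rucaparib until values have returned to Grade 2 or better, then resume rucaparib with a dose reduction". No bilirubin condition is attached. The Grade 3 guidance is limited to patients without other signs of liver dysfunction, and it allows continued dosing only if bilirubin is below ULN.

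**Interruption limits.** Section 5.4.2.1 requires discontinuation after more than 2 weeks off drug for toxicity, unless the case is discussed with the Protocol Chair. Section 5.4.2.1.2 repeats the limit without that exception. Its paragraph on intercurrent events unrelated to toxicity or progression allows 4 weeks before discussion with the Principal Investigator.

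**The concern.** This is the protocol's removal rule for a serious liver signal, and two sites that both follow the text can act differently on the same laboratory report. One may remove the man when the result arrives because he is a PHL case by name. Another may wait for the cause review because the bracket asks for it. A third, with a Grade 4 transaminase in front of it, may follow the ALT/AST paragraph and plan to resume. While the cause is open, the appendix to which sites are referred does not say whether rucaparib is held or given, and the limits on a hold differ between sections.

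What is at stake is mainly patient safety and consistent conduct across sites. It also affects how discontinuations are classified and reported.

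**Working it through.** The plan gives no figure to reproduce. The check sets the passages side by side, with one piece of arithmetic.

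**Step 1: name against criterion.** PHL needs the two laboratory thresholds. HL needs the two thresholds and no other cause. Section 6.4 carries the PHL name and the HL content. For a man who meets both thresholds:

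| Situation | 6.4 read by name | 6.4 read by bracket |
|---|---|---|
| Cause not yet known | removed on the result | not yet removed |
| Another cause found | removed | not removed |
| No other cause found | removed | removed |

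The two readings agree only in the last row. Appendix F section 6 provides for a man with a second on-treatment PHL episode, which is hard to square with removing every man at his first. It does not settle what Section 6.4 means.

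**Step 2: the Grade 4 rule.** Take a man with Grade 4 ALT or AST and bilirubin at least 2 times ULN. The ALT/AST paragraph has him hold until Grade 2 or better and then resume at a lower dose. Section 6.4 removes him by name in all cases, and by bracket if no other cause is found. Neither text refers to the other.

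**Step 3: does any section direct continued dosing?** The combined signal needs bilirubin at least 2 times ULN. The only explicit continuation rule needs bilirubin below ULN. No patient can meet both at once, so the answer is no. Appendix F is silent on dosing rather than permissive.

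**Step 4: the two clocks.**

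- Review period (Appendix F section 5): 3 weeks × 7 = 21 days from detection, with provision for longer delay.
- Restart limit (Section 6.4): 14 days after a cessation for an adverse event.
- If drug is held from detection and the review uses its full allowance: 21 − 14 = 7 days during which the limit has passed and the cause is still open.
- If drug is not held, the 14-day clock does not start.

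The hold is not hypothetical. The Grade 4 rule orders it, and Section 5.4.2.1.2 orders an interruption for any Grade 3 or 4 event judged related.

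**Step 5: a man held from detection and cleared on days 15 to 21.**

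- Section 6.4: already past the 14-day limit, with no exception stated.
- Section 5.4.2.1.2, toxicity limit: past 2 weeks, with no exception stated.
- Section 5.4.2.1: past 2 weeks, but open to discussion with the Protocol Chair.
- Intercurrent-event paragraph: 4 × 7 = 28 days, so still inside the limit if the other cause makes this a non-toxicity interruption.

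The outcome depends on which paragraph the site opens.

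**The case against.** The strongest defence is that the Section 6.4 bullet states its own criterion on the same line, so a site must ignore the bracket to remove a man on laboratory values alone. On that view the mismatch is one of labelling. The review period is also not unmanaged: under Appendix F the Study Physician contacts the investigator to agree the follow-up, and Section 6.4 lets the treating physician stop for unacceptable events. The ALT/AST rules are introduced as suggested guidelines, and a man already removed has no resumption step to follow. The 3-week figure is an upper limit, and the 14-day limit runs only after a cessation.

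Much of this is fair, and it narrows the point. It does not remove it: the label still contradicts the appendix that defines it, the Grade 4 paragraph still has no bilirubin exception or cross-reference, and agreeing an approach case by case is not a stated dosing rule.

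Three stronger inferences are tempting, and the documents do not support them.

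- **That some section tells sites to keep dosing through the combined signal.** Step 3 shows that none does. The repeat-episode section does not show it either, because a man who was held, cleared and restarted fits its wording equally well.
- **That a man cleared after day 14 cannot be kept on treatment.** The Protocol Chair exception and the 4-week paragraph both offer a route, although Section 6.4 acknowledges neither.
- **That the primary endpoint is biased.** A PSA50 response counts only on rucaparib, and one patient is 1/28 = 3.6 percentage points of the planned 28. That is merely the weight of any single patient, and it is zero if he would not have responded. Section 1.2.5 describes the ALT/AST rises seen so far as not accompanied by significant bilirubin changes, so combined cases should be rare.

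**Conclusion.** The point stands as an inconsistency between stated rules for one safety signal. Section 6.4 supports two readings that differ whenever the cause is unknown or another cause is found. The Grade 4 ALT/AST rule and Section 6.4 give different actions for the same man when the bilirubin criterion is also met. Appendix F leaves dosing unstated during a review that can outlast the 14-day restart limit by 7 days or more.

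The 7-day figure assumes that drug is held from detection and that the review takes its full 3 weeks; a faster review or no hold removes the overlap. The documents give no frequency for the combined signal, so the number of patients affected cannot be estimated beyond saying it is likely to be small. The case for acting rests on having a clear safety rule, not on a calculated effect on the response rate.

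**What to change.** Reconcile Section 5.4.2.1, Section 5.4.2.1.2 (toxicity limit, ALT/AST paragraph and intercurrent-event paragraph), Section 6.4 and Appendix F in one amendment:

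1. In Section 6.4, use one Appendix F term together with the definition that Appendix F gives it.
2. In Appendix F, state the dosing status while the cause review is open. Make the review period compatible with the restart limit, and say which interruption limit and which exception govern a hold for this reason.
3. In the Grade 4 ALT/AST paragraph, state how the rule relates to Section 6.4 when the bilirubin criterion is also met.

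Which clinical rule applies at each point is for the sponsor and the medical monitor to decide; this review proposes none. The cost is protocol wording and the usual amendment approval, with no extra tests, staff or patients.
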